7. TREATMENT AND FOLLOW UP

7.1 Study drug: dosage and interval

Enrolled participants will receive an intra-nodal injection of 4 µg GAD-alum three times. The first, second and third injection will be 1 month apart (Table 1). GAD-alum will be injected directly into an inguinal lymph node by a qualified radiologist at the X-ray department of the study site by help of ultrasound technique. The responsible investigator or study nurse will inspect the injection site prior to administration of GAD-alum. The patient shall remain in the vicinity of the study site for the next hour after the injection, and the injection site will be investigated again by the responsible investigator or study nurse 1 hour post injection. Attempts will be made to inject GAD-alum into the same lymph node each time. The time of the day for injection will be decided by the cooperating radiologist.

Supplementation with vitamin D starts at day -30 if the vitamin D serum levels are below 100 nmol/L (40ng/ml) at screening. If the patient has vitamin D serum levels above 100 nmol/L (40 ng/ml) at screening, no vitamin D supplementation will be given to that patient. Patients with vitamin D levels below 100 nmol/L (40 ng/ml) at screening will receive vitamin D (2000 IE per day) administered orally for 4 months (120 days in total). The patient should be instructed to return all unused vitamin D blisters/boxes at Visit 6.

7.2 Intervention

Patients will be followed for a total of 12 months during which their endogenous insulin production and immune response will be evaluated at regular intervals throughout the study period. A physician and a study nurse will be responsible for carrying out the events of the study. Study procedures and assessments are described in Table 1. Urine and blood samples will be taken for safety, diabetes status assessments, vitamin D levels and immunological assessments. Concomitant medication and demographics will be collected.

7.3 Discontinuation criteria

The sponsor/investigators reserve the right to discontinue the study at any time for safety reasons or for other reasons jeopardizing the justification of the study. Such a termination will be implemented in a time frame that is compatible with the patient's wellbeing.

If the study is prematurely terminated or suspended, the investigator should promptly inform the patients and assure appropriate therapy and follow up. The sponsor will notify the Regulatory Authorities and the Ethics Committee of any plans to terminate the study.

7.4 Supply of study drug

GAD-alum will be supplied as prepacked medication from Diamyd Medical (Stockholm, Sweden) to a local pharmacy (in Trondheim: Sykehusapoteket at St Olavs Hospital, in Stockholm: Pharmacy at Karolinska University Hospital, Solna, Stockholm). All dosing will take place in the hospital and handled only by trained and authorized study personnel. GAD-alum will be stored in a refrigerator at 2-8°C in a secure area (e.g. a locked cabinet or drug store room), protected from unintended use. The GAD-alum solution must never be frozen (i.e. exposed to temperatures below 0°C). If any temperature deviations occur, please contact Diamyd Medical immediately ([contact]) and do not administer any GAD-alum solution that have been exposed to temperatures outside the acceptable temperature range without prior approval from Diamyd Medical.

7.5 Supply of non-investigational medicinal product

Vitamin D will be purchased and labeled by the local hospital pharmacy (in Trondheim: Sykehusapoteket at St Olavs Hospital, in Stockholm: Pharmacy at Karolinska University Hospital, Solna, Stockholm). It will be ordered through the electronic prescription system by the PI and picked up by the study participant at the local hospital pharmacy. The vitamin D used in the study will be:

Trade name: "Divisun 2000 IE", Supplier: In Stockholm: Meda, Solna, Sweden, in Trondheim: Meda, Allerød, Denmark.

Vitamin D kits should be stored at room temperature (< 25 °C) in a secure area (e.g. a locked cabinet or drug storage room), protected from unintended use at the pharmacy.

All study medication will be labelled with information according to national and local regulations.

7.6 Study drug and non-investigational medication product accountability

GAD-alum and vitamin D must be retained in a safe place at all times of the study. Only personnel authorized by the responsible investigator will dispense GAD-alum and vitamin D, and the accountability is the responsibility of the responsible investigator.

The patient should be instructed to return all unused vitamin D in the blisters/boxes at Visit 6 and compliance to the vitamin D supplementation should be checked.

GAD-alum and vitamin D inventory (dispensing records) must be maintained at all times and always kept current. Used and unused medication must be stored at the site or at the pharmacy throughout the study. The investigator/pharmacist must keep record of the GAD-alum and vitamin D received, used and returned. Both the pharmacy and the study site are obliged to properly measure and record the storage temperature.

When the study is completed all unused and used study medication must be returned to the drug supplier unless the drug supplier has approved other arrangements. The remaining vitamin D will be handled and disposed of by the local pharmacies. **NB!** Before any study drug and

non-investigational medication product is returned and destructed the used vials and blisters/boxes should be monitored and accountability performed.

8. ASSESSMENT OF EFFICACY

8.1 Effect parameters

See also Section 5.2, secondary endpoints. Endogenous insulin production will be measured by glucagon- and mixed meal stimulation of C-peptide at baseline and after 5 and 12 months of intervention. Metabolic control will be evaluated by measurements of HbA1c and fasting glucose at all study visits. Immunological response will be assessed by measurements of GADA and the immunological parameters listed in Section 5.2. Blood samples for the assessment of immunological response will be collected at all study visits.

8.2 Methods for the recording of effect parameters

The patient must attend all study visits in the morning following an overnight fast (>10 hours, water allowed). Each visit should be completed as scheduled (see Table 1). However, for patients with evidence of an infection, the visit should be postponed until the patient has recovered.

8.2.1 *Endogenous insulin production: Visit 2, 3, 6 and 7*

The MMTT [37] and the GSCT [36] must be performed according to the instructions in the specific laboratory manuals. The tests must be carried out on separate days, as each test has to be performed in the fasting state. Also, if the patient develops need for insulin treatment during the study period, the patient must not take short acting/direct acting insulin within 6 hours before the test. The patient is allowed to take base-insulin the day/night before, but not in the test morning and during the MMTT and the GSCT. If the patient does not fulfill the above mentioned criteria, the MMTT and GSCT should be rescheduled and the patient return to the study site within 5 days if possible.

MMTT: The patient will be given a standardized liquid nutrition mixture. Blood samples will be secured for glucose and C-peptide measurements at before and 0, 30, 60, 90 and 120 (± 5) minutes after the meal.

GSCT: The patient will receive an intravenous injection of 0.5 mg glucagon. Blood samples will be secured both before and 6 minutes after the injection for the measurements of glucagon-stimulated C-peptide and glucose.

8.2.2 *Immunological tests: Blood samples collected at all visits: Visit 2-7*

Measurements of GADA titer and some of the relevant immunological parameters will be performed at the Department of Clinical and Molecular Medicine, NTNU. Measurements of Anti-SARS-CoV-2 will be performed at Laboratoriemedisinsk klinikk, St Olavs Hospital, Trondheim, and at Karolinska Universitetslaboratoriet, Stockholm. HLA classification will be

performed at Oslo University Hospital Rikshospitalet, Department of Immunology and Transfusion medicine. Classification and analyses of T-cells and other relevant immunological tests will be performed at Linköping University Hospital.

9. SAFETY AND ADVERSE EFFECTS

9.1 Safety parameters

See also Section 5.1, Primary endpoint, and Table 1.

The safety assessments include occurrence of adverse events (AEs), laboratory measurements, physical examinations including neurological assessments. Adverse events will be recorded by the physician at every visit throughout the study.

Blood tests for safety:

- Chemistry: Creatinine, Calcium, Liver function tests (alanine aminotransferase (ALT), aspartate aminotransferase (AST), alkaline phosphatase, bilirubin)
- Haematology (MHC, MCV, MCHC, Haemoglobin, Platelets, Leukocytes)

Urinalysis for safety:

- Urine pregnancy test as appropriate
- Microalbuminuria
- Creatinine

Other Variables which will be evaluated:

- Inflammatory markers, especially TNF-alfa, IL-1 beta, IL-2, IL-17
- Th2-deviation of cell-mediated immune response seen e.g. as increased ratio of IL-5,10, 13 in comparison with IFN-gamma, TNF-alfa, IL-1 beta and IL-17, and increase of T-regulatory cells
- C-peptide (90 minute value and AUC mean 0-120 min) during an MMTT
- Fasting C-peptide
- HbA1c
- D-vitamin
- Antibodies against SARS-CoV-2 (at Visit 6 and 7)

9.2 Definitions of adverse events and reactions

An adverse event (AE) is defined as any untoward medical occurrence in the clinical trial subject administered a medicinal product and which does not necessarily have a causal relationship with this treatment. An adverse event can therefore be any unfavorable and unintended sign (including an abnormal laboratory finding, for example), symptom or disease temporally associated with the use of a medicinal product, whether or not considered related to the medicinal product.

A serious adverse event (SEA) is defined as any untoward medical occurrence or effect that at any dose results in death, is life-threatening, requires hospitalization or prolongation of

existing hospitalization, results in persistent or significant disability or incapacity, or is a congenital anomaly or birth defect.

These characteristics/consequences have to be considered at the time of the event. For example, regarding a life-threatening event, this refers to an event in which the subject was at risk of death at the time of the event; it does not refer to an event which hypothetically might have caused death if it were more severe.

Some medical events may jeopardize the subject or may require an intervention to prevent one of the above characteristics/consequences. Such events (referred to as *important medical events*) should also be considered as serious in accordance with the definition.

A suspected unexpected serious adverse reaction (SUSAR) is defined as a SAE, the nature or severity of which is not consistent with the applicable product information (e.g. investigator's brochure for the unauthorized investigational product).

The term 'severity' is used here to describe the intensity of a specific event. This has to be distinguished from the term 'serious'. The term severe is used to describe the intensity (mild, moderate or severe) of the event and the event does not necessarily need to be considered serious. The term serious is based on the patient/event outcome or action and serves as a guide for defining regulatory reporting obligations.

Mild intensity: The adverse event is transient and easily tolerated.

Moderate intensity: The adverse event causes the patient discomfort and interrupts the patient's usual activities.

Severe intensity: The adverse event causes considerable interference with the patient's usual activities and may be incapacitating or life-threatening.

9.3 Relationship to study medication

Relationship to study medication will be assessed for the two treatments (Diamyd and Vitamin D) separately. AEs with a causal relationship assessment of Unlikely related, Possibly related and Probably related will be considered to be Adverse Reactions.

Not related: This category is applicable to those AEs which, after careful medical consideration at the time they are evaluated, are judged to be clearly and incontrovertibly due to extraneous causes (disease, environment, etc.) and do not meet the criteria for study medication relationship listed under remote, plausible or probable.

Unlikely related: Time relationship non-existent or doubtful and/or other factor(s) certain or probable to have been causative.

Possibly related: Time relationship exists. Other possible causative factor(s) may exist (e.g., concurrent disease or concomitant medication). Improvement on dechallenges or dose reduction may or may not have been seen.

Probably related: Time relationship exists. No other possible causative factor(s) may exist (not reasonably explained by the patient's known clinical state or concomitant medication). Improvement on dechallenges or dose reduction (if performed) has occurred. Recurrence of symptoms on rechallenge (if performed) has occurred. A specific laboratory investigation (if performed) has confirmed the relationship.

9.4 Reporting and follow up of adverse and serious adverse events (AE and SAE)

All AE must be recorded in the CRF, defining relationship to study medication, severity and seriousness. AE should also be recorded by the physician or study nurse in the patient file/notes.

Timelines and Reporting of SAE

All SAEs must be reported, whether or not considered attributable to the study drug on a separate SAE Report Form. SAEs will be reported from signing of informed consent.

TFS Trial Form Support AB (TFS) will be responsible for reporting all SAEs in accordance with ICH Good Clinical Practice (GCP) and local regulations. Diamyd and TFS will complete and sign a “Pharmacovigilance Working Agreement” agreement covering the safety reporting responsibilities in the study. This agreement will ensure the sponsor is directly informed of each SAE reported by the investigators.

In order to meet the specified reporting requirements investigators should adhere to the following process for recording and reporting SAEs.

It is the investigator's responsibility to, as soon as he/she is aware of a potential SAE, contact TFS by fax or e-mail, and in any case no later than 24 hours after the knowledge of such a case. At the time of initial reporting, the investigator must provide as a minimum requirement, the patient number, birth date, nature of the SAE, and a preliminary assessment of causality. The investigator should follow-up the initial notification of the potential SAE by faxing or e-mailing a copy of the SAE reporting form to TFS at the numbers/e-mail address provided in the investigator Site File and on the SAE Report Form. The faxed/e-mailed SAE Reporting Form should be received by TFS within 24 hours of the initial notification of the event.

It is the investigator's responsibility to report to TFS follow-up information on an existing SAE that is fatal or life-threatening within 5 days after the initial report. Where appropriate, hospitalization or autopsy reports should be made available. All SAEs will be followed up until resolution (i.e., asymptomatic, stabilization or death).

It is TFS's responsibility to receive e-mail or fax copies of the SAE report form and other relevant eCRF pages from the investigators. The Drug Safety unit at TFS will review the information provided on the form and enter it into the safety data base. The SAE report will be

assigned a unique number that will be entered on the SAE Report Form and will be used to identify the report in all future communication. A notification of receipt of the report will be sent to the reporter, either by fax or e-mail within 48 hours. TFS will contact the investigator directly if there is any inconsistencies and missing information.

TFS is responsible for the timely submission of SUSARs to the Competent Authorities and IECs according to appropriate Competent Authority and IEC requirements. It is TFS's responsibility to report SUSARs to investigators according to ICH GCP and to local regulations. Competent Authorities will be notified of all SUSARs through the EudraVigilance database.

Fatal and life-threatening SUSARs should be reported by TFS as soon as possible to the Competent Authorities and Ethical Committees in Norway and Sweden, and in any case no later than seven (7) calendar days, after knowledge by the Sponsor/TFS of such a case. Relevant follow-up information on the case will be subsequently communicated within an additional eight (8) days. All other SUSARs shall be reported to the Competent Authorities concerned and to the Ethics Committee concerned as soon as possible but within a maximum of fifteen (15) days of first knowledge by TFS.

Pregnancy Report Form

Pregnant and lactating women will not be included in the study. Females of childbearing potential must have a negative urine pregnancy test prior to randomization and a negative urine pregnancy test at each study visit with Diamyd administration, prior to injection of the study drug. Patients will be required to use an adequate form of birth control during the study. At Visit 2 the need for birth control will be re-assessed. Patients and their partners will be strongly advised to avoid pregnancy for 1 year following the last dose of Diamyd and instructed to use adequate birth control.

A pregnancy occurring during the trial must be recorded on the Pregnancy Report Form and no further drug doses will be given. If the pregnancy is verified prior to any of the injections, no further injection shall be given.

The Pregnancy Report Form should be faxed or e-mailed within 24 hours of awareness to TFS. A copy of the report should be filed at the study site for follow-up until delivery. Any pregnancy must be followed until delivery or to the end of pregnancy.

9.5 Annually report of AE/SAE

Sponsor shall annually send the authorities in both Norway and Sweden

- a) a list of all assumed serious adverse events that have occurred in the period in question, and
- b) a report on the safety of the trial subjects.

10. STATISTICS

10.1 Statistical analysis plan

In brief the following analyses are planned:

All continuous variables will have the following descriptive statistics displayed: Number of observations (n), mean value, standard deviation, minimum, median and maximum. All variables of a categorical nature will be displayed with frequencies and percentages. The tabulation of the descriptive statistics will be split by visit. Where appropriate, baseline (screening) descriptive statistics will also be included.

Demographic and other baseline characteristics will be presented using descriptive statistics (summary tables).

Variables. The AE/SAE data will be presented using a standardized tabulation of the frequency and incidence rate of all observed AE/SAEs. The frequencies and incidence rates are calculated on a per patient basis. Adverse events will be summarized by body system, causality and severity. Other safety data will be presented as descriptive statistics.

Data regarding immune response, beta cell function, AE and other data will be summarized descriptively.

Analyses of data will be performed after 5 and 12 months from baseline. Data from the BALAD study (see Section 3.3.1) will be used as a historical control for the evaluation of treatment-related effects on the evolution of beta cell function parameters between baseline and 5 and 12 months of intervention. We acknowledge that it is difficult to statistically compare data from BALAD as a historical control with data from this pilot study, as the participants in BALAD were randomized to active treatment. The comparison will still be valuable, primarily as a pointer for future research.

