5. TRIAL DESIGN

5.1 Primary endpoint

Variables for the evaluation of safety and feasibility:

- 1) Injection site reactions, skin reactions 1 hour post injection vs. before injection.
- 2) Occurrence of AEs, continuously registered and status summarized at 5 and 12 months after the first injection.
- 3) Laboratory measurements (hematology and clinical chemistry), status summarized at 5 and 12 months after the first injection vs. baseline.
- 4) Physical examinations, including neurological assessments, status summarized at 5 and 12 months after the first injection vs. baseline.
- 5) GAD65A titer in serum, levels at 5 and 12 months after the first injection vs. baseline.
- 6) Vital signs (blood pressure), status summarized at 5 and 12 months after the first injection vs. baseline.

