6.4 Withdrawal criteria

a) When and how to withdraw subjects from the trial

In accordance with the Declaration of Helsinki, the investigator must explain to the patient that they have the right to withdraw from the study at any time, and that this will in no way prejudice their future treatment. The reason for any kind of withdrawal must be recorded in the CRF.

There will be two main categories for withdrawals from the study:

Complete withdrawal (i.e. stopping investigational product(s) and also continued efficacy and safety evaluations). In order to achieve as complete as possible 12 month follow-up, whenever feasible, patients that are considered for complete withdrawal should be asked if they could consider to return for a 12-month visit. Attempts should be made to contact patients lost to follow-up with respect to this.

Standard reasons for withdrawing from further participation in the study and from the follow-up visits may be:

- Patient's decision (withdrawal of consent to participate)
- Patient lost to follow-up

Withdrawals from investigational product(s) (i.e. stopping one or several investigational products, but continuing follow-up visits, including efficacy and safety evaluations)

Standard reasons from withdrawing from taking further investigational product, but continuing follow-up visits and safety evaluations may be:

- Unacceptable AEs
- Patient request
- Investigator's discretion
- Patient lost to follow-up/non-attendance
- Intercurrent illness
- The patient becomes pregnant

Criteria for terminating the investigational product treatment/trial treatment:

Rapid increase in HbA1c or decline in C-peptide levels vs. historical controls. Evidence for induction of stiff person syndrome (SPS) or any adverse neurological or behavioural effects.

GAD-alum should not be given to the patient if the patient after inclusion in the study develops/experiences:

- Brain damage, epilepsy, head trauma, neurological disease
- Any active, serious hormonal disease other than LADA
- Other severe autoimmune disease (except celiac disease which is accepted for inclusion)
- Immune-suppressive treatment
- Cancer, cancer treatment
- Any vaccination
- Drug/alcohol abuse
- Becomes pregnant or is no longer willing to use safe contraceptives during the study

Vitamin D supplementation should not be continued if the patient after inclusion in the study develops/experiences:

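### The planned AE summary in section 10.1 is per patient only, so it cannot show whether a reaction recurs after the second and third injection

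*Combined protocol and SAP*

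**What the plan says.** Section 10.1 promises a "standardized tabulation of the frequency and incidence rate of all observed AE/SAEs". It then fixes the unit: "The frequencies and incidence rates are calculated on a per patient basis". The breakdown follows: "Adverse events will be summarized by body system, causality and severity". It mentions no number of events, no injection after which an event began, no count of injections given and no recurrence within a patient. It also does not say how a patient with repeated events is counted.

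The table serves primary variable 2 in section 5.1: "Occurrence of AEs, continuously registered and status summarized at 5 and 12 months after the first injection".

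Other provisions bear on the point:

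- Section 7.1 and Table 1 give each patient three injections, at Visits 3, 4 and 5, 30 days apart with a tolerance of 5 days.
- Section 9.3 includes in its probably-related category: "Recurrence of symptoms on rechallenge (if performed) has occurred".
- Section 10.1 has a general rule, "The tabulation of the descriptive statistics will be split by visit", but does not say whether it covers the AE table.
- Section 5.1, item 1, makes skin reactions one hour after injection a separate primary variable.
- Section 6.4 lets patients stop injections and stay in follow-up, keeps withdrawn patients in the safety analysis, and promises listings of all patients' data.

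**The concern.** The regimen exposes each patient to the same antigen three times. Whether an event comes back, or comes back worse, after the next injection is among the few internal signs of causality available here. There is no placebo arm (5.3), and section 10.1 uses BALAD as a historical control for beta cell function, not for AEs.

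If the AE summary reports only how many patients had an event, a reaction that recurs with each injection looks like an isolated one. Section 5.3 makes the absence of safety concerns one condition for moving to a placebo-controlled trial, so the summary behind that judgement should be able to show the pattern.

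**Working it through.** **Inputs.** About 15 patients (10.2) and three injections each (7.1), hence at most 15 × 3 = 45 injections. The documents state no AE rate and no power calculation, so there is no plan figure to reproduce. The numbers of reactors and stoppers below are assumptions for illustration.

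**1. Per patient against per injection.** Per-patient rate = patients with at least one event / 15. Per-injection rate = injections followed by the event / 45.

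| Assumed pattern | Per patient | Per injection |
|---|---|---|
| 3 patients react once | 3/15 = 20.0% | 3/45 = 6.7% |
| 3 patients react every time | 3/15 = 20.0% | 9/45 = 20.0% |
| 5 patients react once | 5/15 = 33.3% | 5/45 = 11.1% |
| 5 patients react every time | 5/15 = 33.3% | 15/45 = 33.3% |

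The exact (Clopper-Pearson) 95% interval for 5/15 is 11.8% to 61.6%, the same for both five-patient patterns. A threefold difference in events does not show in the per-patient column.

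**2. Do other provisions supply the missing information?**

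- *The two summary times.* The third injection is at about day 60. The summaries fall at about days 150 and 360, so both cover all three injections together.
- *The by-visit rule.* If it applied to AEs, events reported at Visits 4 and 5 would follow injections 1 and 2. It would still not show whether the same patient had the same event again. The reporting periods would also be unequal: about 30, 30, 90 (150 − 60) and 210 (360 − 150) days.
- *The skin inspection.* It is tied to each injection but covers only skin reactions at one hour. Later local, systemic and neurological events reach the summary through the AE table.
- *Causality.* Recurrence appears only in the probably-related definition, which also requires that no other cause be possible. A recurring event with another possible cause fits the possibly-related category, whose definition does not mention recurrence.
- *Listings.* Recurrence could be read from them by hand, but that is not a planned summary.

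**3. The denominator.** Suppose two patients stop because of an AE and two others react. The proportion ever affected is 4/15 = 26.7%. Removing the stoppers would lower it to 2/13 = 15.4%. All treated patients therefore belong in the per-patient table. A different denominator is needed only for a rate tied to a later injection. If three stop after injection 1 and three patients react to injection 3, the rate among recipients is 3/12 = 25.0%, against 3/15 = 20.0%.

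**4. The window for a table by injection.** About 30 days follow injections 1 and 2, but about 360 − 60 = 300 days follow injection 3. Assume a constant background of 2 to 4 AEs per patient-year (the documents give none) and P(at least one) = 1 − exp(−rate × days/365):

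- 30 days: 1 − exp(−0.164) = 15% to 1 − exp(−0.329) = 28%.
- 300 days: 1 − exp(−1.644) = 81% to 1 − exp(−3.288) = 96%.

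Assigning every event to the most recent injection would thus create a false build-up. The window must be the same length after each injection.

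**The case against.** The best defence is that the information is not lost. AEs are recorded at every visit (9.1), injection sites are inspected around each injection, rechallenge can enter the causality assessment, and all patients' data are listed. With about 15 patients, a careful reader could find recurrence in the listing. Section 10.1 also never says that a patient is counted once. That is the usual meaning of a per-patient basis, but it is an inference. All of this stands, and it limits the point to the planned summary. It does not remove it, because none of these provisions reports recurrence as a result for primary variable 2.

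A reader might infer three stronger points. The documents do not support them:

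- *Recurrence vanishes from the trial.* It does not. The data are collected and listed, and the AE table is produced at 5 and 12 months rather than once for the whole trial.
- *Patients who stop injections dilute the AE rate.* Not in the planned table. No injection-2 or injection-3 rate is specified, treated patients belong in a proportion ever affected, and those who stop for an AE are in its numerator.
- *An any-AE row would be close to 100% whatever the product does.* Section 10.1 names no such row, and the argument needs background rates that the documents do not give.

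**Conclusion.** The point holds as a weakness of the planned AE summary, not of data collection or of the safety population. On the usual reading, the only AE rate specified in section 10.1 gives the same result for one reaction per affected patient and for three. In the illustration with five affected patients, 33% per patient stands for either 11% or 33% per injection. This matters because the primary objective is the safety of a repeated injection, there is no AE control, and the protocol itself counts recurrence towards causality.

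The conclusion rests on two things: that a per-patient basis means patients with at least one event, which the plan should state, and that the general by-visit rule would not report within-patient recurrence even if it applied to AEs. The numbers of reactors are illustrative. The direction of the result does not depend on them. The change is worth making before the 5-month analysis.

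**What to change.** In section 10.1, keep the per-patient table with all treated patients in the denominator, and state that it counts patients with at least one event. Add:

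- (a) the number of events beside the number of patients;
- (b) AEs with onset within the same fixed window after each injection (about 30 days, the dosing interval), with the patients who received that injection as denominator and later events shown separately. Because Table 1 allows 5 days either way, the interval can be as short as 25 days, so say how an event is assigned when the next injection falls inside the window;
- (c) the number of patients in whom the same event recurred after a later injection, and in how many the severity rose.

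The cost is a few extra table columns, with no additional patients or visits. One check is needed first. For AEs, section 9.4 names relationship, severity and seriousness as CRF items but not the onset date, so confirm that onset dates are recorded in the CRF.
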